## 4 STATISTICAL ANALYSES

### 4.1 General

we will perform an intention to treat analysis using mixed effect analysis.

### 4.2 Statistical Analysis Plan

Statistical analysis will be undertaken using PRISM version 9.3.1. All analyses will be conducted on an intention-to-treat principle using all randomised participants in the groups they were originally randomised to. A blinded statistician will perform the data analysis. In the per-protocol analysis only patients complying with the treatment protocol are included in the statistics, this means that the patient has received all per-protocol injections and performed at least 75% of the training program.

A blinded statistician will perform the data analysis.

Demographic and anthropometric characteristics (gender, age, mass, height, body mass index, sporting activities and pain duration) will be determined at the baseline visit for each treatment group.

Statistical analyses will be conducted on 1, 2, 3, 6, 9 and 12 months on all outcome measures. However, the primary end-point will be total score and subscores of the VISA-A questionnaire at 6 months.

Between-group comparisons of treatment effect for all primary and secondary outcomes, will be performed with a mixed effect analysis. To assess for superiority, mean between-group differences in changes from baseline and two-sided 95% confidence intervals will be calculated.

The ordinal scaled data of patients overall assessment of the treatment effect (Lickert score -5 to +5) will be analyzed with mixed effect analysis, if the data is found normally distributed.

The ordinal scaled data of grading the flow within the tendon into 4 categories will be calculated using non parametric statistics: Mann-Whitney U-tests.

Return to sport in percent of earlier sports activity will be compared using unpaired t-test if the data is normally distributed, otherwise non parametric analysis (Mann-Whitney) is performed.

A two-sided P value of less than 0.05 will be considered to indicate statistical significance.

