### **Secondary outcome measures**

Lickert scale at 1, 2, 3, 6, 9 and 12 months: 11 point box scale from -5 to +5, where 0 is the status at entry, +5 is cured, and -5 is much worse.

VISA-A scores (total and pain subscales) at 1, 2, 3, 9 and 12 months.

Thickness of the Achilles tendon measured by ultrasound scan, cross-sectionel image on the thickest of the tendon at 1, 2, 3, 6, 9 and 12 months. The thickness of the "healthy" tendon is also measured for comparison.

Ultrasound Scanning Doppler Activity assessed with Color Doppler at 1, 2, 3, 6, 9 and 12 months.

After 6, 9 and 12 months, it is also assessed how many percentage of previous activity level (from before the injury) they have recovered. The patient himself states this as a percentage.

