## 6 SAMPLE SIZE AND POWER

The risk of finding a difference between groups, even if there really is none, is set at 5% (risk of type I error), while the risk of overlooking a difference between the groups that is actually present is set at 20% (type II error). Individual changes from baseline over time will be calculated and all outcome parameters analyzed using mixed effect analysis. Q-Q plots will be visually examined prior to analysis to ensure that the assumption of normal distribution is not violated. Significance level is set to 0.05.

The minimum relevant difference in VISA-A is set at 15. Based on other studies on pain intensity, we expect a baseline mean of 50. Standard deviation is estimated to be 16 on VISA-A. Power of 80% provides a sample size of 20 participants in each group. We will include 25 patients in each group in case of data loss and no-shows, thereby including a total of 50 patients.

The primary analysis will be blinded and follow the intention-to-treat principle with baseline values as covariates. but we will also perform a per-protocol analysis only including patients performing at least 75% of the training programs and receive the per-protocol injections. No interim analyses will be made.

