#### **4.4 Timing of analyses**

When this statistical analysis plan was signed, recruitment to the trial had started, but analysis had not been initiated.

Statistical Analysis Plan  
Exercise/Injections in Achilles entesopathy

	Enrolment	Allocation	Month 1	Month 2	Month 3	Month 6	Month 9	Month 12
TIMEPOINT**	June 2021 – end June 2023	June 2021 – end June 2023					March 2022 end 2024	June 2022 end 2024
ENROLMENT:								
Eligibility screen	X	X						
Informed consent		X						
Allocation		X						
INTERVENTIONS:								
Intervention group			◆	◆	◆	◆		
Control group			◆	◆	◆	◆		
ASSESSMENTS:								
Diagnosis		X						
VISA-A		X	X	X	X	X	X	X
Morning pain [VAS]		X	X	X	X	X	X	X
Pain after activity [VAS]		X	X	X	X	X	X	X
Return to usual sports participation						X	X	X
Satisfaction with result of treatment			X	X	X	X	X	X
Patient diary for reporting compliance and adverse events			◆	◆	◆			
Ultrasound examinations		X	X	X	X	X	X	X
Demographics		X						

Table 1: SPIRIT figure. Schedule of enrolment, interventions and assessments

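### Does section 4.2 leave baseline adjustment open for tendon thickness and for VISA-A at the visits other than month 6?

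*SAP*

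**What the plan says.** Section 4.2 sets one model for everything: "Between-group comparisons of treatment effect for all primary and secondary outcomes, will be performed with a mixed effect analysis". For superiority it adds that "mean between-group differences in changes from baseline and two-sided 95% confidence intervals will be calculated". It names no covariate. It then gives Doppler grade and return to sport their own tests, and makes the mixed model for the Likert scale conditional on normality.

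Section 6 has the only mention of baseline adjustment: "The primary analysis will be blinded and follow the intention-to-treat principle with baseline values as covariates". The text continues "but we will also perform a per-protocol analysis", limited to patients who complied with training and injections.

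The secondary outcomes include "VISA-A scores (total and pain subscales) at 1, 2, 3, 9 and 12 months" and "Thickness of the Achilles tendon measured by ultrasound scan". The schedule in Table 1 (section 4.4) places VISA-A and "Ultrasound examinations" at allocation, so a baseline value exists for both.

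**The concern.** An analyst who works from section 4.2 alone finds a change-from-baseline contrast and no covariate. If the primary analysis in section 6 means only VISA-A at month 6, nothing tells that analyst to adjust the other VISA-A visits or tendon thickness. An unadjusted change score and a baseline-adjusted contrast would then both satisfy the plan.

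Two things would be at stake. The first is precision: apart from the small cost of estimating one slope, the unadjusted change score never has the smaller variance, and with 50 patients a wider interval can matter. The second is analyst choice: if both analyses were run and the significant one reported, the false-positive rate for that comparison would exceed 5%.

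**Working it through.** **1. Does a change-from-baseline contrast exclude adjustment?** No. Write Y0 for baseline, Y1 for follow-up and T for treatment. The model Y1 − Y0 = a + bT + cY0 rearranges to Y1 = a + bT + (c + 1)Y0. The treatment effect b and its standard error are the same. Sections 4.2 and 6 are therefore compatible for the primary endpoint.

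**2. The plan's own figure.** Section 6 gives a difference of 15, SD 16, two-sided 5% and 80% power. Then n = 2 × (1.960 + 0.842)² × 16² / 15² = 17.9, so 18 per group, or 19 with the t distribution. The stated 20 is sound and does not depend on this point.

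**3. Precision with equal SDs.** The SAP gives neither the correlation ρ between baseline and follow-up nor a follow-up SD, and does not say whether 16 is the SD of the score or of the change. Assume 16 is the score SD at both visits, 25 per arm, complete data and a single visit.

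- Unadjusted: SD of change = 16√(2(1 − ρ)), 48 df.
- Adjusted: residual SD = 16√(1 − ρ²), 47 df, variance multiplied by 1 + 1/46 for the covariate.
- Half-width = t(0.975) × SD × √(2/25), with that multiplier under the root for the adjusted analysis.

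Example at ρ = 0.3: unadjusted 2.011 × 18.93 × 0.2828 = 10.77; adjusted 2.012 × 15.26 × 0.2828 × √1.0217 = 8.78.

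| ρ | Unadjusted half-width | Adjusted half-width | Narrower by | Variance ratio |
|---|---|---|---|---|
| 0.3 | 10.77 | 8.78 | 18% | 1.51 |
| 0.5 | 9.10 | 7.97 | 12% | 1.31 |
| 0.7 | 7.05 | 6.57 | 7% | 1.15 |
| 0.9 | 4.07 | 4.01 | 1.5% | 1.03 |

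**4. Precision with a larger follow-up SD.** With general SDs s0 (baseline) and s1 (follow-up), the excess variance of the unadjusted score is (s0² + s1² − 2ρs0s1) − s1²(1 − ρ²) = (s0 − ρs1)². It approaches zero as ρs1 approaches s0, which can happen if patients respond unevenly and scores spread out. The SDs below are assumed.

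| s0 / s1 | ρ | (s0 − ρs1)² | Unadjusted half-width | Adjusted half-width |
|---|---|---|---|---|
| 16 / 22 | 0.7 | 0.36 | 8.94 | 9.04 |
| 12 / 20 | 0.5 | 4.00 | 9.92 | 9.96 |
| 16 / 20 | 0.7 | 4.00 | 8.20 | 8.21 |

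Here the cost of the covariate cancels or slightly outweighs the gain.

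**5. Selective reporting.** Simulation with no true effect, 25 per arm and 20,000 trials per setting: each test alone rejects in about 5% of trials. With SD 16 at both visits, at least one of the two rejects in 7.8%, 7.4% and 6.7% at ρ = 0.3, 0.5 and 0.7 (Monte Carlo error about 0.2 points). For 16/22 at ρ = 0.7 and 12/20 at ρ = 0.5 the rates are 5.5% and 5.7%.

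**6. What the text supports.** The covariate clause in section 6 is followed at once by the per-protocol alternative, so primary there distinguishes the intention-to-treat analysis from per-protocol. It speaks of baseline values in the plural, in a section that has just referred to all outcome parameters, and section 4.2 applies intention to treat to every analysis. Section 6 also describes changes over time, and section 4.2 analyses every visit by mixed model. On the ordinary reading, VISA-A is one repeated-measures model, month 6 is one contrast from it, and a baseline covariate in that model serves the other visits too.

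**The case for a change.** The strongest case for acting is that the estimator is the SAP's own business and the remedy is one sentence. Under Primary outcome measures and in section 4.2, primary also labels the endpoint at month 6, so the narrow reading of section 6 is possible. The SAP does not spell out that all VISA-A visits come from one model. If the correlation is 0.3 to 0.5 and the SDs are equal, intervals 12% to 18% narrower are worth having in a trial of 50. Analysis under labels A and B would not stop someone preferring the analysis that reaches significance, because a difference between A and B is visible before the code is broken.

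Part of this stands: section 4.2 does not repeat the covariate, and for tendon thickness adjustment is nowhere expressly stated. The rest carries less weight. The large gains belong to VISA-A, where the one-model reading largely closes the gap. Thickness may well be highly correlated over time, and the gain at 0.9 is about 1.5%. The inflated error rate assumes a practice that no section of the SAP plans, namely running both analyses and reporting whichever is significant.

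**Conclusion.** No change to the plan is called for. This is missing detail in secondary outcomes, which an analyst would fill from section 6. It is not a contradiction, introduces no bias, and leaves the primary endpoint and the sample size untouched. The difference in precision runs from about 18% in interval width (equal SDs of 16, correlation 0.3) through about 1.5% (correlation 0.9) to none (larger follow-up SD, such as 16/22 at correlation 0.7). All of these rest on assumed correlations and SDs, and on a single-visit comparison with complete data. The conclusion rests on reading the primary analysis in section 6 as the intention-to-treat analysis, and the VISA-A visits as contrasts from one mixed model. Both are the natural readings, though the text does not make either explicit.

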#### Inclusion criteria

1. Ultrasound diagnosed Achilles entesopati.
2. In ultrasound scanning, the affected Achilles tendon must be trumpet-shaped thickened in the attachment (enthesis) and with increased flow in the tendon itself.
3. Duration of pain should be a minimum of 3 months
4. Participants are from 18 years to 65 years.
5. Participant may provide relevant and adequate informed consent.

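### The Mann-Whitney comparison of the 4-category Doppler flow grade makes no stated use of baseline flow and so may give up some precision on one secondary outcome

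*SAP*

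**What the plan says.** Section 4.2 of the SAP fixes the method for flow: "The ordinal scaled data of grading the flow within the tendon into 4 categories will be calculated using non parametric statistics: Mann-Whitney U-tests". It names no covariate, stratum or change score.

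Three other places bear on baseline flow:

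- The inclusion criteria require that "the affected Achilles tendon must be trumpet-shaped thickened in the attachment (enthesis) and with increased flow in the tendon itself", so flow is looked at before treatment.
- Table 1 in section 4.4 has a row "Ultrasound examinations", marked at allocation and at months 1, 2, 3, 6, 9 and 12.
- The secondary outcome list has "Ultrasound Scanning Doppler Activity assessed with Color Doppler at 1, 2, 3, 6, 9 and 12 months". It gives no baseline Doppler assessment.

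For the primary analysis, section 6 says that it will "follow the intention-to-treat principle with baseline values as covariates". Sections 6 and 4.2 also contain general sentences that send all outcomes to mixed effect analysis of changes from baseline. The flow sentence is a specific exception to them.

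**The concern.** A Mann-Whitney test on the grade at a visit compares the arms as if nothing were known about flow at entry. If a patient's flow at follow-up depends on flow at entry, two things follow. Part of the spread in follow-up grades is predictable and could be removed, which would raise power. And with about 25 patients per arm, a chance difference in baseline flow carries over into the comparison in proportion to the correlation.

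The plan already accepts this reasoning for its primary analysis. At stake is the precision of the Doppler result at six visits. The VISA-A analysis and the sample size are not affected.

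**Working it through.** **The plan's own figure.** The SAP gives no power calculation for flow. Its only sample size is for VISA-A: difference 15, SD 16, two-sided 5%, power 80%. The formula n = 2 × (1.960 + 0.842)² × (16/15)² gives 17.9, so 18 per group (19 with the t distribution), against 20 stated. Then 20 / (1 − 0.20) = 25 enrolled per group. The figure reproduces within 2 patients and has no bearing on this point, except that it puts the analysed number between 20 and 25 per arm.

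**Inputs for flow.** From the SAP: four ordered grades, two equal arms, two-sided 5%, increased flow at entry. Assumed, because the SAP is silent: 23 per arm, a latent normal scale cut at quartiles into four grades, a treatment shift of 0.75 latent SD, and a latent correlation of 0 to 0.7 between baseline and follow-up. The SAP does not say which grades count as increased flow, so baseline was limited to the upper 3 or the upper 2 grades.

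**Tests compared.** Mann-Whitney: normal approximation with tie and continuity correction. Quade: rank the follow-up grades (Ry) and the baseline grades (Rb) over both arms, fit Ry = a + b × Rb, take residuals e = Ry − (a + b × Rb), and compare e between arms with an unpaired t-test.

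**Power, Mann-Whitney / Quade (%), 20,000 simulated trials per cell:**

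| Correlation | Upper 3 grades | Gain | Upper 2 grades | Gain |
|---|---|---|---|---|
| 0 | 62.1 / 61.6 | −0.5 | not tabulated | about 0 |
| 0.3 | 64.6 / 65.6 | 1.0 | 65.6 / 66.2 | 0.6 |
| 0.5 | 68.5 / 73.0 | 4.5 | 71.3 / 73.7 | 2.4 |
| 0.7 | 74.5 / 84.9 | 10.4 | 80.0 / 84.8 | 4.8 |

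The Monte Carlo standard error of each figure is at most √(0.25 / 20,000) = 0.35 points. A repeat of the upper-2 setting gave gains of about 1, 3 and 6. Moving the cut-points, with baseline in the upper 3 grades, gave 1.4, 4.3 and 10.5 (follow-up cut at cumulative 40/70/90%) and 1.8, 5.5 and 12.3 (baseline cut at 10/70/90%). The range therefore shifts by about 2 points with that assumption.

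**What the gain is worth.** Using power ≈ Φ(δ − 1.96), so δ = 1.96 + Φ⁻¹(power), the squared ratio of the two δ approximates the equivalent gain in sample size. At correlation 0.5 this is (2.573 / 2.442)² = 1.11 for upper 3 and (2.594 / 2.522)² = 1.06 for upper 2. At 0.7 it is (2.992 / 2.619)² = 1.31 and (2.988 / 2.802)² = 1.14. The narrower the baseline grades, the less there is to adjust for.

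**Type I error.** At 20, 23 and 25 per arm it was 4.4-5.1% for Mann-Whitney and 4.6-5.3% for Quade.

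**Alternatives**, at 25 per arm, shift 0.9, upper 3 grades, 2,000 trials per cell, correlations 0 / 0.3 / 0.5 / 0.7:

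| Test | Power (%) |
|---|---|
| Mann-Whitney on grade | 79.3 / 83.1 / 87.0 / 90.5 |
| Mann-Whitney on change in grade | 58.0 / 72.4 / 84.1 / 94.9 |
| Van Elteren, stratified by baseline grade | 77.1 / 82.4 / 88.5 / 95.8 |
| Quade | 78.7 / 84.3 / 90.2 / 96.4 |

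Change in grade is worse than the raw grade at correlations up to 0.5. Van Elteren gives up about 2 points at correlation 0, and Quade about half a point.

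**The case against.** The strongest reply is that nothing here is an error. Mann-Whitney suits a four-category ordinal outcome, randomisation makes the unadjusted test valid, and section 6 ties baseline covariates to the primary analysis only. That stands. A reader might infer that the flow sentence contradicts the baseline rule, but the documents do not support this: an unadjusted secondary test is compatible with an adjusted primary one.

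Second, the general wording on changes from baseline could mean that the test is applied to change in grade. The flow sentence names the grade itself, and the change wording is attached to mixed effect analysis, so the raw grade at each visit is the more natural reading. It remains a reading. The firm statement is that the SAP does not say how baseline flow is used.

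Third, a recorded baseline grade is not shown. The entry criterion is met or not met, the outcome list starts at month 1, the Table 1 row is generic, and the baseline characteristics in section 4.2 leave out flow. It is therefore too strong to say that the plan discards a grade it holds. The fix has to be conditional.

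Fourth, the size depends on a correlation that the documents do not give. With a weak correlation, or a narrow range of baseline grades, there is almost nothing to gain. This also stands.

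**Conclusion.** The point holds as a modest matter of efficiency, to be considered rather than required. Under the stated assumptions, baseline adjustment gains about 0 power points at correlation 0, 1-2 at 0.3, 2-5 at 0.5 and 5-10 at 0.7, and costs at most about half a point. It concerns one secondary outcome.

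Two larger claims might be inferred and should not be. With no restriction on baseline grade, the gain at correlation 0.7 reaches 81.4 − 62.0 = 19.4 points, but the entry criterion rules that population out. And in the 7% of null trials where the arms differ by chance by 0.4-0.6 of a grade at baseline (upper 3 grades), Mann-Whitney gives 5.8%, 8.4% and 13.1% false positives at correlations 0.3, 0.5 and 0.7. In the 35% of trials with a difference below 0.1 it gives 4.4%, 3.7% and 2.6%. Averaged over all trials, the error stays near 5%, so the planned test is not anti-conservative.

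**What to change.** First establish whether a baseline flow grade on the 4-point scale was recorded, and say so in the SAP.

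- **If it was recorded:** make the Doppler comparison at each visit baseline-adjusted, by Quade's rank analysis of covariance or a van Elteren test stratified by baseline grade. Quade lost less at weak correlation in the figures above. Report the planned Mann-Whitney test alongside as a sensitivity analysis.
- **If it was not recorded:** keep Mann-Whitney as the main test.
- **In either case:** state that the test is applied to the grade at each visit, not to the change in grade, and that the flow grade is an exception to the general mixed-model sentences.

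The cost is a sentence or two of SAP wording and, per visit, two rankings, one simple regression and one unpaired t-test. No new data are needed if the grade exists. Section 4.4 says that analysis had not begun at signing; the change should be made before any grouped data are examined.

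The downsides are little gain if the correlation is weak or baseline grades are narrow, loss of patients without a baseline grade from the adjusted test, and, as with Mann-Whitney, no mean difference in grade.

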### **Trial Design**

Triple-blinded parallel group randomized superiority controlled trial with follow-up at 1,2, 3, 6 and 12 months. 25 patients are included in each of the 2 groups. If people are included and receive treatment from the doctor, but do not show up for the first follow-up after 1 month, they will be replaced. Patients leaving the trial after 1 month of follow-up will not be replaced.

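### Return to sport gets a two-sample test that uses only patients seen at that visit, although the plan promises mixed-effect analysis of all outcomes in all randomised participants

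*SAP*

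**What the plan says.** Return to previous activity level is a secondary outcome (SAP Section 5, Secondary outcome measures): "After 6, 9 and 12 months, it is also assessed how many percentage of previous activity level (from before the injury) they have recovered". No baseline value is collected; Table 1 shows the first assessment at month 6.

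Three general statements cover its analysis:

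- Section 4.2, on the method: "Between-group comparisons of treatment effect for all primary and secondary outcomes, will be performed with a mixed effect analysis". Section 6 says the same: "all outcome parameters analyzed using mixed effect analysis".
- Section 4.2, on the population: "All analyses will be conducted on an intention-to-treat principle using all randomised participants in the groups they were originally randomised to".
- Section 4.2, on timing: "Statistical analyses will be conducted on 1, 2, 3, 6, 9 and 12 months on all outcome measures".

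Section 4.2 then has a sentence for this outcome alone: "Return to sport in percent of earlier sports activity will be compared using unpaired t-test if the data is normally distributed", and Mann-Whitney if not.

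On losses, Trial Design says: "Patients leaving the trial after 1 month of follow-up will not be replaced". Section 6 plans for some: "We will include 25 patients in each group in case of data loss and no-shows". The SAP gives no imputation or other missing-data rule.

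**The concern.** The specific sentence does not fit the general ones. A two-sample test takes one value per patient, so it has to be run visit by visit on whoever has a value then. It is not a mixed-effect analysis and, with no missing-data rule, it cannot use all randomised participants once anyone is missing.

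Two things are at stake. First, information already collected is discarded: someone who answered at months 6 and 9 contributes nothing at month 12. Second, if patients who do poorly leave more often in one arm, the comparison among those remaining is distorted, and the month-6 answers that could partly correct it go unused. The late visits have some clinical interest, because the SAP Introduction cites a steroid trial with relapse after 6 months.

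**Working it through.** **The plan's own figure.** The only sample-size calculation is for VISA-A: difference 15, SD 16, two-sided 5%, power 80%. n = 2 × (1.96 + 0.84)² × 16² / 15² ≈ 17.9, so 18 per group; the t-distribution version gives 18.87, so 19. The stated 20 is consistent with this and is not disputed. Its use here is the loss allowance: 25 included for 20 needed, or 5/25 = 20% per group.

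**The sentences side by side.**

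| Question | General rule | Return to sport |
|---|---|---|
| Method | Mixed-effect, all outcomes (Sections 6 and 4.2) | t-test or Mann-Whitney (4.2) |
| Patients used | All randomised (4.2) | Only those with a value at that visit |
| Visits | Each time point (4.2) | Months 6, 9 and 12 (Section 5, Table 1) |
| Missing values | No rule | No rule |

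The Doppler flow grade, assigned Mann-Whitney in Section 4.2, has the same conflict.

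**Precision.** Let f be the fraction missing at month 12 and ρ the correlation between month 12 and an earlier visit. ρ is assumed; the SAP gives none. If every missing patient was seen earlier, the large-sample variance of an arm mean, relative to full data, is:

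- single-visit test: 1/(1 − f) = 1/0.8 = 1.25
- model using the earlier value: 1 + [f/(1 − f)] × (1 − ρ²)
  - ρ = 0.7: 1 + 0.25 × 0.51 = 1.1275
  - ρ = 0.8: 1 + 0.25 × 0.36 = 1.09

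The standard-error ratio at ρ = 0.7 is √(1.1275/1.25) = 0.95.

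Now suppose only half of the 20% were seen earlier. The analysed set is 90% of the arm, and 0.1/0.9 of it is missing at month 12. The factor at ρ = 0.7 is (1 + 0.125 × 0.51)/0.9 = 1.18, and the standard-error ratio is √(1.18/1.25) = 0.97. If none were seen earlier, the factor stays at 1.25 and nothing is gained.

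**Bias.** If leavers average g points below stayers, the observed-case difference is off by g × (difference in loss rates). With assumed losses of 5/25 and 1/25, the difference in rates is 0.16:

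- g = 10: 1.6 points
- g = 20: 3.2 points
- g = 30: 4.8 points
- equal loss and equal g in both arms: 0

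For scale, at an assumed SD of 25 the standard error with 20 and 24 patients is 25 × √(1/20 + 1/24) ≈ 7.6 points.

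**How much a model could remove.** A simulation with 400,000 per arm assumed means of 60, 65 and 70, SD 25, ρ = 0.7 and no true difference. In one arm only, some patients below 40 at month 6 left.

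| Loss in that arm | Observed-case difference, month 12 | Using the month-6 value |
|---|---|---|
| 8% | 2.1 | −0.07 |
| 13% | 3.4 | −0.09 |
| 19% | 5.7 | 0.01 |

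This is the most favourable case: every leaver was seen at month 6, and leaving depended only on that value.

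**The case against.** The strongest reply is that Section 4.2 sets a default and then gives outcome-specific rules, so an analyst knows which test applies to return to sport. The default is also framed as change from baseline with baseline as a covariate, and this outcome has no baseline, so a different method is understandable. That largely settles which test is meant. It does not settle the clash with the promise to use all randomised participants, and the SAP does not label the sentence an exception. Nor does a missing baseline rule out a mixed model: the −5 to +5 overall assessment, which has no baseline measurement because 0 is entry status by definition, is given one when normally distributed.

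Three stronger readings are tempting, and the documents do not support them:

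- A reader might infer that most losses have occurred by month 6. The SAP does not give the timing of loss. If it were so, most leavers would have no return-to-sport value and the model would not help them.
- A reader might infer that the planned comparison is biased by about 5 points. That figure rests wholly on an assumed gap and assumed unequal losses, and it is below one standard error at an SD of 25.
- A reader might infer that a mixed model would deliver the all-randomised promise. It would not: patients with no value at months 6, 9 or 12 stay out, and leaving driven by unobserved outcomes still biases the result.

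**Conclusion.** The inconsistency stands on the SAP's own wording, and it is minor. For this outcome the specified test cannot meet the stated analysis population once values are missing, and it leaves repeated answers unused.

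The gain from changing it is modest. At ρ = 0.7 and 20% missing at month 12, the standard error falls by about 5% if all the missing patients were seen earlier, about 3% if half were, and not at all if none were. Bias is reduced only as far as leaving is explained by earlier return-to-sport values. The correlation, the share seen earlier and the leaving pattern are assumptions; the 20% is the plan's own allowance. The point concerns a secondary outcome; the primary VISA-A analysis at 6 months is unaffected.

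**What to change.** In SAP Section 4.2:

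1. Make the main analysis of return to sport one mixed-effect model of months 6, 9 and 12, with group, visit and group-by-visit terms, reporting the group difference with its 95% confidence interval at each visit. State that it has no baseline or change-from-baseline term because none is collected.
2. Keep the plan's fallback: if the residuals are clearly non-normal, use Mann-Whitney at each visit on observed cases, described as such.
3. Describe the analysed set as randomised patients with at least one return-to-sport value, and report by arm how many have none.
4. Reword the all-outcomes statements in Sections 4.2 and 6, and the all-randomised statement in 4.2, so that the exceptions are named, including the Doppler grade.

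The cost is a few sentences in the SAP and one more model of a type already planned. No new data are needed, and Section 4.4 says that analysis had not begun when the plan was signed.
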